10.4.2 ANALYSIS OF THE PRIMARY EFFICACY ENDPOINT(S)

Co-Primary Endpoint(s): Arrival to qualified ED within 30 minutes

The proportion of qualifying episodes to arrive at the ED within 30 minutes will be compared to our historical data point estimate of 38.7% using a one sample exact test of binomial proportions at the 0.05 two-sided significance level.

Co-Primary Endpoint(s): Initiation of ECPR within 30 minutes of ED arrival

Using the modified intention to treat population with ongoing cardiac arrest in the qualified ED, we will declare the analysis of this objective successful if 80% or more of patients have ECPR (qualifying ED standard care process) initiated within 30 minutes of ED arrival. No formal hypothesis test will be conducted.

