	Exploratory: Neuropsychological and cognitive testing using NIH toolbox
	Exploratory: Time to vascular access and time to ECPR cannulation
Population:	Out-of-hospital cardiac arrest patients who do not have return of spontaneous circulation after initial rhythm analysis by first- responders who can potentially arrive at a qualified ED in persistent cardiac arrest within 30 minutes of initial 911 call or EMS witnessed first cardiac arrest.
Phase:	2
Number of Sites	
enrolling participants:	1
Description of Study Interventions :	Patients in the field will be randomized to either early transport to the hospital versus standard care (continued attempts at advanced cardiac life support in the field). Standard clinical procedures in the hospital will be followed for refractory cardiac arrest patients.
Study Duration:	30 months
Participant Duration:	Three months

SCHEMATIC OF STUDY DESIGN

EMS = emergency medical services, CPR = cardiopulmonary resuscitation, mCPR = mechanical CPR, eCPR = extracorporeal CPR, ACLS = advanced cardiac life support, ROSC = return of spontaneous circulation, TOR = termination of resuscitation, SR = shockable rhythms, ED = emergency department, UM = University of Michigan

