5.1.1 PATIENT LEVEL INCLUSION

- Present with out-of-hospital cardiac arrest, presumed non-traumatic etiology, requiring CPR
- Age presumed or known to be 18 through 70 years old (prior to 71st birthday)
- Predicted arrival time at ECPR-capable hospital within timeframe specified
- Initial shockable rhythm (ventricular tachycardia or ventricular fibrillation) or witnessed pulseless electrical activity or asystole
- Persistent cardiac arrest after initial cardiac rhythm analysis and shock (if shock is indicated)

Participants will be enrolled in the study if they meet initial inclusion criteria at the time of their cardiac arrest.

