5.3 STRATEGIES FOR RECRUITMENT AND RETENTION

There is no participant “recruitment” for this study as it is not possible to prospectively identify victims of out-of-hospital sudden cardiac arrest and obtain informed consent. Participants will be included in the study if they meet enrollment criteria at the time of their cardiac arrest. Based on historical data, we anticipate randomizing 30 refractory OHCA patients over 18 months. This clinical trial will be conducted under exception from informed consent (further details in Section 13).

Patients will be screened and assigned a randomization group at the time of dispatch. Study eligibility and randomization will be further determined with the aid of an algorithm or expected time to eligible hospital map where a 911 dispatch operator will input eligibility data points and receive one of 3 responses. This is pre-enrollment treatment group assignment. Despite assignment to one of these three groups, the patient will not be considered randomized until they have met the inclusion criteria (including the refractory nature of the cardiac arrest.)

1. Not eligible continue usual resuscitative care (stay in place until ROSC or resuscitation

meets termination criteria)

2. Eligible, randomized to usual care (operationally same as 1 for paramedics)
3. Eligible, randomized to early transport

After an initial rhythm assessment and shock delivery (if indicated), patients who do not have ROSC will be considered randomized. Based on the assignment given at the time the prehospital providers were dispatched, they will either continue usual care (stay in place until ROSC) if assigned to that group (control), or undergo expedited transport with mechanical CPR device in place (experimental group). Patients who do not meet inclusion criteria or have exclusion criteria will not be considered randomized or enrolled, since no experimental procedures will occur to them (standard procedure is for patients to be transported after ROSC). If ROSC is achieved during transport or in the emergency department (experimental group), they will be included in the primary analysis of the expedited transport group. All patients will be followed for clinical outcomes.

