7.3 STUDY SCHEDULE

7.3.1 SCREENING

Screening (Day 0, Field Baseline)

Screening will be done by prehospital providers in all out-of-hospital cardiac arrests in the engaged agencies area. All out-of-hospital cardiac arrests, meeting inclusion criteria will be considered for the study.

Pre Enrollment – Treatment Group Assignment / Randomization

At the time of dispatch of EMS, the dispatcher will enter the address of the arrest, age of the patient, and time of 911 call into a web form. The form will use an application to determine whether the patient is within the travel distance to arrive at the hospital within the pre-specified interval. They will immediately receive one of the following messages:

- 1) Not eligible, continue usual resuscitative care (patient may be out of geographic time area, may be over 71 years old)
- 2) Eligible, randomized to usual care
- 3) Eligible, randomized to early transport.

If the dispatcher is unable to access the assignment/randomization website, there will be a study team member, with access rights to the website available by telephone at all times.

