10.2 STATISTICAL HYPOTHESES

- Co-Primary Endpoint(s): Arrival to qualified ED within 30 minutes

We hypothesize that the proportion of patients randomized to early transport arriving at the hospital within 30 minutes will be greater than the historical proportion of 38.7%.

- Co-Primary Endpoint(s): Initiation of ECPR within 30 minutes of ED arrival

We hypothesize that greater than or equal to 80% of patients will have ECPR (qualifying ED standard care process) initiated within 30 minutes of ED arrival.

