10.5 SAMPLE SIZE

Based on 2014 data, we expect approximately 20 unique visits in one year to qualify, thus in 18 months we expect 30 patients to qualify with the protocol used on at least 24 (80%) of these. With 24 patients, if we find that 19/24 (79.2%) of cases meet time limit we have 98% power to find that the proportion of patients arriving at the ED within 30 minutes is significantly different than in 2014. The protocol will be deemed optimal if $\geq 19/24$ patients are transported to the ED within 30 minutes (95% CI lower bound 62.6%).

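### The 38.7% null value does not reconcile with the roughly 20 qualifying visits in section 10.5, and the plan does not show that it fits a population selected on predicted 30-minute arrival

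*Combined protocol and SAP*

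**What the plan says.** Section 10.2 hypothesises that the proportion of patients randomized to early transport and "arriving at the hospital within 30 minutes will be greater than the historical proportion of 38.7" per cent. Section 10.4.2 makes this a two-sided test at 0.05 in which the observed proportion "will be compared to our historical data point estimate of 38.7% using a one sample exact test of binomial proportions". The other co-primary endpoint has no formal test, and the secondary, subgroup and exploratory analyses have none either.

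Section 10.5 sets the sample size: "Based on 2014 data, we expect approximately 20 unique visits in one year to qualify". It projects 30 patients in 18 months, with the protocol used in at least 24. It then states that, with 19/24 arriving in time, "we have 98% power to find that the proportion of patients arriving at the ED within 30 minutes is significantly different than in 2014". It also calls the protocol optimal if at least 19 of 24 arrive within 30 minutes.

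Eligibility uses the same clock. Section 5.1.1 lists "Predicted arrival time at ECPR-capable hospital within timeframe specified". The synopsis gives the timeframe by describing patients "who can potentially arrive at a qualified ED in persistent cardiac arrest within 30 minutes of initial 911 call". In section 7.3.1 a dispatch application is used to "determine whether the patient is within the travel distance to arrive at the hospital within the pre-specified interval". Sustained ROSC is an exclusion (5.2), and section 5.3 notes that "standard procedure is for patients to be transported after ROSC".

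No section says which visits produced 38.7%.

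**The concern.** A one-sample test against a fixed value is sound only if that value is the rate expected without the intervention in the kind of patient being tested. Section 10.4.1 says that randomization is not meant to create comparable groups, so the control arm is not there to correct a benchmark that does not fit.

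Two eligibility rules bear directly on the endpoint:

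- The travel-time filter removes patients predicted to arrive too late. If the historical base includes such visits, the matched rate is above 38.7%, and the arm can beat 38.7% without faster transport.
- The no-ROSC rule removes patients who would ordinarily have been moved. Section 2.3.2 says that current practice in refractory arrest is to stop in the field. The general cardiac arrest protocol in the appendices restricts transport without ROSC, and section 5.3 agrees. If the historical base includes ROSC patients, the matched rate is below 38.7%, and the test may miss a real gain.

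The figures in 10.5 suggest that the base of 38.7% is not the set of visits expected to qualify, which is why the fit cannot be taken for granted.

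**Working it through.** **Inputs.** Null 0.387 (10.2, 10.4.2); exact binomial, two-sided 0.05 (10.4.2); n = 24 and alternative 19/24 = 0.792 (10.5); about 20 qualifying visits a year from 2014 data (10.5).

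**1. The plan's own power.** With X ~ Binomial(24, 0.387), the upper rejection region is X ≥ 15 under both the equal-tail and the minimum-likelihood definition of the exact p-value. P(X ≥ 15 | 0.387) = 0.0156. P(X ≥ 15 | 19/24) = 0.983. The stated 98% reproduces, given its inputs.

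**2. Which counts give 38.7%.** I looked for k/n with 38.65 ≤ 100k/n < 38.75. There is none for n ≤ 30. The first are 12/31, 24/62 and 29/75. Near 20, 7/19 = 36.8%, 8/20 = 40.0% and 8/21 = 38.1%. So a simple proportion rounded to one decimal needs a base of at least 31, against about 20 in section 10.5.

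**3. What a mismatch would do.** The matched rate p, meaning the in-time rate without the protocol in patients passing the trial's criteria, is not in the documents. It is ranged here as an assumption. *Upward rejection* is P(X ≥ 15 | 24, p), the chance that the planned cut declares a gain when there is none. *Matched cut* is the smallest upper count significant at two-sided 0.05 against p itself. *Power* is P(X ≥ matched cut | 24, 19/24). *Optimal rule* is P(X ≥ 19 | 24, p).

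| Assumed matched rate p | Upward rejection at ≥15/24 | Matched cut | Power at 19/24 with matched cut | Optimal rule, ≥19/24 |
|---|---|---|---|---|
| 35% | 0.5% | 14 | 99% | <0.1% |
| 38.7% | 1.6% | 15 | 98% | <0.1% |
| 45% | 6.5% | 16–17 | 89–95% | 0.1% |
| 50% | 15.4% | 18 | 78% | 0.3% |

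At 45% the cut is 16 by minimum likelihood (power 95%) and 17 by equal tails (power 89%).

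For a larger mismatch in the other direction, take p = 25%. The matched cut is then 11. A real rise to 50% would be detected with probability P(X ≥ 11 | 0.5) = 73% by the matched cut, but with P(X ≥ 15 | 0.5) = 15% by the planned one.

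**4. Precision of a small benchmark.** If the matched count were 8/20, its exact 95% CI would be 19% to 64%. For 12/31 it would be 22% to 58%.

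**The case against.** The strongest reply is that the figure of 20 in section 10.5 is a forecast of yearly yield. It is not a list of visits already screened, and it is not stated to be the denominator of 38.7%. That is right. A base of 31 visits that all met the travel-time filter, of which about 20 a year would qualify after age, DNAR/DNI, opt-out, agency and similar criteria (5.1.1, 5.1.2, 5.2), would fit 38.7%, 2014 and the 20 together. Exclusions of that kind may hardly move the in-time rate. So it does not follow that 38.7% must come from visits too far away, and a reader should not infer it. What stands is that the plan does not say this, and nothing printed lets a reader choose between the explanations. A base of 31 visits over 18 months would annualise to 20.7, but 10.5 speaks of 2014 and of one year.

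A reader might also infer a badly inflated false-positive rate. Starting from 12/31 and removing 11 late visits leaves 12/20, where the planned cut rejects upward 48.9% of the time. That requires every removed visit to be late and none on time, on an assumed base. The statements on transport in 2.3.2, 5.3 and the appendix point the other way for patients without ROSC, so the documents do not support this figure as an estimate.

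Finally, the 19/24 rule in 10.5 is a stricter standard: even at a true 60% it is passed by chance only 4.0% of the time. That protects the judgement that the protocol is optimal. It does not protect the formal test, which can be reported as significant from 15/24.

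**Conclusion.** The concern holds as a failure to reconcile and a missing justification. The null value in 10.2 and 10.4.2 and the 2014 yield in 10.5 cannot both describe the same visits, if 38.7% is a simple proportion rounded to one decimal and *approximately 20* means fewer than 31. Because enrolment selects on the predicted endpoint and on absence of ROSC, the source of 38.7% decides whether the test has its stated properties.

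The documents do not show that 38.7% is wrong, what the matched rate is, or on which side of 38.7% it lies. The travel-time filter would raise the matched rate, the no-ROSC rule would lower it, and other exclusions may do little. Across assumed matched rates of 35% to 50%, the planned cut rejects upward without improvement in 0.5% to 15.4% of trials, and the appropriate cut runs from 14 to 18 of 24. The 98% power is computed correctly but depends on 38.7% being the right null. This should be corrected because it concerns the trial's only formal test.

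**What to change.** Apply the trial's eligibility criteria and travel-time filter to the 2014 visits behind 38.7%. Count those that reached the qualified ED within 30 minutes on the trial's clock (911 call or provider-witnessed arrest), and use that proportion as the null in 10.2, 10.4.2 and 10.5. Print its numerator, denominator and exact 95% CI, and restate the critical count and the power. The one-sample exact test can stay.

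If 38.7% already comes from visits passing that filter, keep it, print its numerator and denominator, and correct or explain whichever of *2014* and *approximately 20* in 10.5 does not describe the same data.

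The cost is one tabulation and a few edited figures, with no added patients and no new test. It assumes that the 2014 records hold what the dispatch application uses (address, age and time of the 911 call, section 7.3.1) and the ROSC status. There are two drawbacks. A benchmark from about 20 visits is imprecise, as the 19% to 64% interval for 8/20 shows. And if the matched rate exceeds 40%, the stated power falls, for example to 78% at 50%.

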2.2 RATIONALE

Currently available evidence suggests that ECPR for OHCA should be initiated within 60 minutes of cardiac arrest onset to maximize the potential therapeutic benefit. Therefore, in addition to delivering patients to the ED within 30 minutes, it is essential that our system of care is able to initiate ECPR within ≤ 30 minutes of ED arrival. In a recently published study of ED-initiated ECPR, the median time from ECPR team arrival to initiation of ECPR was 20 minutes [IQR 15-30 minutes] [Stub 2014]. The goal is to achieve < 30 -minute arrival to cannulation for all patients meeting inclusion/exclusion criteria for ECPR therapy.

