4 STUDY DESIGN AND ENDPOINTS

4.1 DESCRIPTION OF THE STUDY DESIGN

4.2.1 Primary Endpoints

Co-Primary Endpoint: Time interval from 911 call or prehospital witnessed first cardiac arrest (qualifying OHCA event) to ED arrival in minutes.

The primary endpoint was selected because the goal of the study is to demonstrate the feasibility of transporting patients with refractory OHCA to an ECPR-capable ED within 30 minutes of the 911 call or EMS witnessed arrest.

Co-Primary Endpoint: Time interval from ED arrival to ECPR initiation in minutes

This time interval was chosen because the apparent therapeutic window for OHCA ECPR is 60 minutes and time from ED arrival to ECPR flow is estimated to be 30 minutes.

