- Past medical history; known comorbidities
- Nurses notes
- Tests performed and their results
- Procedures performed and their outcome
- Status of ECPR procedure
 - Time of confirmed placement of arterial and venous ECMO catheters
 - Time of initiation of ECPR
- ED Discharge diagnosis
- ED disposition

Survival to Hospital Admission (Day 0- Hospital Discharge or Death)

Attempt to notify the participant, LAR, or family member of study participation and seek permission to continue in the study, using the written IRB approved informed consent form.

Hospital medical records will be reviewed and the following data abstracted:

- Date and time of Hospital admission
- Status of ROSC
- Use of therapeutic hypothermia
- Neurologic status
- Physician progress note(s)
- Nurses notes
- Tests performed and their results
- Procedures performed and their outcome
- Assess for serious adverse events

Hospital Discharge

Hospital medical records will be reviewed and the following data abstracted:

- Date and time of Hospital discharge
- Survival status
- Assess for serious adverse events
- Discharge disposition

The following assessments will be performed by a member of the study team:

- CPC
- mRS
- NIH Toolbox Cognitive Testing

Assess for Serious Adverse Events (SAE's)

Prehospital and hospital records will be reviewed for serious adverse events.

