10.3 ANALYSIS DATASETS

The analytic datasets will use a modified per-protocol population. Patients who are assigned to early transport and do not have ROSC after initial rhythm analysis (and shock if indicated) and have the early transport initiated will be considered the primary analytic population for the ED arrival endpoint. Patients who are randomized to early transport and remain in cardiac arrest for at least 10 minutes after ED arrival and have the institutional standard care ECPR process initiated are considered the primary analytic population for the ECPR initiation endpoint. Exploratory clinical and safety endpoints will be collected on the entire population of refractory OHCA patients enrolled/randomized to either early transport or usual care.

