- (2) Necessary resources will be determined case-by-case, with necessary available resources including: ECMO specialist or ECMO credentialed emergency department RN dedicated to sitting pump until transfer to CVC; CVC bed to be made available ASAP; ED and EC3 staffing/volume/capacity to care for ECPR patient; Availability of EC3 Intensivist by phone or in person

- (3) Initiation of ECPR includes femoral veno-arterial cannulation by an ECMO surgeon or an emergency physician credentialed for the procedure, as well as circuit and pump management by an ECMO specialist or ECMO-credentialed emergency department RN
- (4) Potential disposition destinations include: Cardiovascular center ICU; cardiac catheterization lab; and/or EC3, if EC3 intensivist and ECMO credentialed RN available

Standard data collected on cardiac arrest patients in UMHS AES

For internal review, quality improvement, and education, the following data elements are among those routinely obtained in patients with cardiac arrest and post-cardiac arrest care delivered in AES:

1. Time intervals, including time of arrest or 911 call, transport time, time of ED arrival, down-time, duration of CPR, time of return of circulation or initiation of ECPR
2. Drugs and shocks administered
3. Method(s) and device(s) used for CPR
4. Method(s) and device(s) used for airway management
5. End-Tidal CO2 measurements
6. Vital sign trends, with attention to diastolic blood pressure measurements when obtained invasively
7. Ventilator parameters, including settings and dynamic measurements
8. Blood gas results
9. Cerebral blood flow index via "C-Flow" device
10. Method(s) of therapeutic hypothermia, when utilized
11. Initial and subsequent cardiac rhythms
12. Return of circulation ECG interpretations
13. Bedside echocardiography images and interpretations
14. Cardiac catheterization results
15. ED, ICU, and hospital length of stay
16. EEG and neuro-prognostication results, including head CT, MRI, SSEP, NSE level, Neurology consultation documentation
17. Cerebral performance category upon discharge

Cardiac Arrest – General

This protocol should be followed for all adult cardiac arrests. Medical cardiac arrest patients undergoing attempted resuscitation should not be transported unless return of spontaneous circulation (ROSC) is achieved or transport is ordered by medical control or otherwise specified in protocol.

- ☑ If an arrest is of a known traumatic origin refer to the **Dead on Scene Protocol**.

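### The ECPR co-primary leaves its clock-stop event undefined and uses nearly the same phrase for numerator and denominator, so a timely but failed attempt may never count as a failure

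*Combined protocol and SAP*

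**What the plan says.** The formal endpoint, in the précis and in 4.2.1, is the interval from ED arrival to ECPR initiation. The plan describes the event that ends this interval in several ways:

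- **Hypothesis (10.2):** "greater than or equal to 80% of patients will have ECPR (qualifying ED standard care process) initiated within 30 minutes of ED arrival".
- **Decision rule (10.4.2):** the objective succeeds "if 80% or more of patients have ECPR (qualifying ED standard care process) initiated within 30 minutes of ED arrival". The section adds: "No formal hypothesis test will be conducted".
- **Justification of the endpoint (4.2.1):** "time from ED arrival to ECPR flow is estimated to be 30 minutes".
- **Rationale (2.2):** "The goal is to achieve < 30 -minute arrival to cannulation for all patients meeting inclusion/exclusion criteria for ECPR therapy".
- **Denominator (10.3):** early-transport patients who are still in arrest at least 10 minutes after ED arrival and who "have the institutional standard care ECPR process initiated are considered the primary analytic population for the ECPR initiation endpoint".
- **Data items (7.3.2):** "Time of confirmed placement of arterial and venous ECMO catheters" and, as a separate item, the time ECPR was initiated. The second item is not defined.
- **Example institutional guideline (Appendix B):** "Initiation of ECPR includes femoral veno-arterial cannulation by an ECMO surgeon or an emergency physician credentialed for the procedure", together with circuit and pump management.

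Section 3 and the précis list cannulation time as an exploratory process measure, distinct from the co-primary.

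**The concern.** A time-to-event threshold needs one time-stamped event. Here the endpoint and analysis sections name an activity that has a duration (initiating a process) and do not say whether its start or its completion counts. They also do not say how to score a patient in whom cannulation is attempted and ECMO is never established.

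The overlap between 10.3 and 10.4.2 makes this more than missing detail. Nearly the same words decide who is analysed and who succeeds. If they mean the same thing in both places, the patients who matter most for feasibility, those with a prompt but unsuccessful attempt, cannot appear as failures.

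The stake is the declaration on a co-primary endpoint. It rests on an observed proportion in a small group, and the trial is unblinded (10.6.2), so the reading could be settled after the results are known.

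**Working it through.** **1. The plan's own figure.** The ECPR co-primary has no power, interval or expected n. The only power figure (10.5) belongs to the ED-arrival endpoint. An exact two-sided 0.05 binomial test with n = 24 and p0 = 0.387 rejects at X ≤ 4 or X ≥ 15. Its power at p1 = 19/24 is 0.983, which reproduces the stated 98% but does not bear on this point.

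**2. One patient under each reading.** Take a patient whose attempt starts at minute 10 and in whom ECMO is never established.

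| Phrase in 10.3 means | Phrase in 10.4.2 means | Result for this patient |
|---|---|---|
| attempt started | attempt started | in the denominator, success |
| ECMO established | ECMO established | not in the denominator |
| attempt started | ECMO established | in the denominator, failure |
| ECMO established | attempt started | not in the denominator |

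Only the third row scores a failure, and it requires the phrase to change meaning between the two sections. A failure would also result if the population in 10.4.2 overrode 10.3. Section 10.4.2 calls its population modified intention-to-treat, while 10.3 announces a modified per-protocol one. The plan does not say which governs.

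**3. How many patients decide the rule.** Successes needed are r = ⌈0.8n⌉, so failures allowed are n − r.

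| n | Failures allowed |
|---|---|
| 5–9 | 1 |
| 10–14 | 2 |
| 15–19 | 3 |
| 20–24 | 4 |

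With 4:1 allocation of 30 patients, early transport has about 30 × 4/5 = 24, so n for this endpoint is at most about 24.

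**4. Illustration from the plan's own background.** In the US ED series in 2.1.2, 18 patients met criteria, 3 regained circulation before ECPR, 8 had ECPR established, 4 could not have catheters placed, and 2 others had fatal placement complications. The denominator is 18 − 3 = 15.

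- Only established ECPR counts: 8/15 = 53.3%, below 80%.
- The 4 failed placements count as initiated: (8 + 4)/15 = 80.0%, which meets the rule.
- The 2 fatal complications count as well: (8 + 4 + 2)/15 = 93.3%.

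Limits: the series gives no timing against the 30-minute limit, and 8 + 4 + 2 + 3 = 17, so one of the 18 is unaccounted for. The last figure assumes that the 2 complications are not among the 8 established. Restricting to the 14 with a reported attempt gives 8/14 = 57.1%, but the comparator is then 14/14 = 100% by construction and is not informative.

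**5. Assumed scenario.** Let q be the true probability of flow within 30 minutes, taken as 0.60 (range 0.50–0.70). If half of the remaining patients are scored as initiated, the success probability becomes q + 0.5(1 − q), which is 0.80 at q = 0.60 (range 0.75–0.85). The chance of meeting the rule is P(X ≥ r):

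| n | r | Only flow counts | Half of failures relabelled |
|---|---|---|---|
| 10 | 8 | 0.167 (0.055–0.383) | 0.678 (0.526–0.820) |
| 15 | 12 | 0.091 (0.018–0.297) | 0.648 (0.461–0.823) |
| 24 | 20 | 0.013 (0.001–0.111) | 0.460 (0.247–0.713) |

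The values of n, q and the relabelled half are assumptions.

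**The case against.** The case on the other side is substantial.

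- The formal event is always ECPR initiation. Flow and cannulation appear only in justification and rationale text, so these are not three rival success definitions.
- Section 6 defines ECPR as veno-arterial ECMO initiated during arrest. A failed cannulation does not obviously satisfy that.
- The parenthesis in 10.2 and 10.4.2 may simply label ECPR as standard care. Section 2.3.1 attaches a similar parenthesis to ECPR.
- Section 7.3.2 records catheter placement separately, and cannulation is exploratory. Appendix B pairs ECPR initiation with return of circulation as one recorded time, and its 60-minute criterion refers to ECMO flow.
- This is a feasibility pilot, and 10.4.10 promises individual tabulation of the primary endpoints.

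Much of this stands. Cannulation is not the co-primary event, and established ECMO is probably what was meant. A reader might infer that the plan does count failed or late cannulation as success; the documents do not support that as a certainty.

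What remains is that none of these places closes the gap. The definition in section 6 itself relies on the word initiated. The 7.3.2 item is undefined. Appendix B is offered as an example and lists activities, not a time stamp. Moreover, if established ECMO is the meaning throughout, 10.3 removes the failed attempts from the denominator, so the objection moves the problem without removing it. Tabulation lets a reader see the analysed intervals, but it does not settle which result is declared.

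**Conclusion.** The numerator and denominator wording is wrong as written. Under either consistent meaning of the shared phrase, a timely attempt that never establishes ECMO is not a failure. That consequence is permitted by the text and not certain, because sections 6 and 7.3.2 and Appendix B favour established veno-arterial ECMO.

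The effect can be decisive. At most 4 failures are tolerated at n = 20–24, and in the cited series the scoring of 4 failed placements alone moves the result from 53% to exactly 80%. That comparison shows sensitivity only. It does not predict this trial's result, since it ignores the time limit and leaves one patient unaccounted for. Severity is moderate: it affects a co-primary declaration, but in a pilot with no formal test of this endpoint and with both relevant times already recorded.

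**What to change.** - In 4.2.1, 10.2 and 10.4.2, define the success event as start of extracorporeal flow within 30 minutes of ED arrival, recorded in the existing ECPR-initiation time item of 7.3.2. Define that item as the start of flow. This matches the endpoint's own justification in 4.2.1.
- In 10.3, state that having the ECPR process initiated means the attempt was started. Attempted but unestablished ECPR then stays in the denominator and counts as not meeting the endpoint. Use the same population name in 10.3 and 10.4.2.
- Keep catheter placement time as exploratory. Reconcile the cannulation wording in 2.2, and use one boundary there (it has both ≤ 30 and < 30 minutes).

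The cost is protocol wording only, because both times are already abstracted. The downside for the sponsor is that the observed proportion may be less favourable.
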